5.1.2 Dose-Interruption, Treatment-Discontinuation, and Study-Withdrawal Criteria

Study-treatment interruption, discontinuation of study treatment, and patient withdrawal from the study due to adverse events will be determined using the criteria listed in [Table 1](#). If any of these criteria are met, treatment will be interrupted (or discontinued, if applicable) and will not be resumed earlier than the next scheduled study visit. The reason for study-treatment interruption or discontinuation should be recorded on the Study Drug Interruption eCRF and, if applicable, on the Adverse Event eCRF.

If a patient misses more than three consecutive doses of study treatment within any 6-month treatment period, the investigator and the Sponsor may consider withdrawing the patient from the study.

Table 1 Dose-Interruption, Treatment-Discontinuation, and Study-Withdrawal Criteria

Event	Dose-Interruption, Treatment-Discontinuation, and Study-Withdrawal Criteria
Intraocular inflammation	
Interrupt study treatment if intraocular inflammation (iritis, iridocyclitis, or vitritis) is $\geq 1+$ in the study eye (see the grading scales of intraocular inflammation in Section 5.3.5 and Appendix 3).
 
Patients with $> 3+$ intraocular inflammation will discontinue study treatment and will be withdrawn from the study.

VA decrease	
Interrupt study treatment if there is a study treatment-related decrease of ≥ 30 letters in BCVA in the study eye compared with the last assessment of BCVA prior to the most recent treatment. Study treatment may be permitted subsequently as determined by the investigator.

Elevated IOP	
Interrupt study treatment if IOP in the study eye is ≥ 30 mmHg. Treatment may be permitted when IOP has been lowered to < 30 mmHg, either spontaneously or by treatment, or as determined by the investigator.

Vitreous hemorrhage	
Interrupt study treatment in the event of a vitreous hemorrhage in the study eye. Study treatment may be permitted subsequently as determined by the investigator.

Rhegmatogenous retinal break	
Interrupt study treatment if a retinal break is present in the study eye. Study treatment may be resumed no earlier than 30 days after successful laser retinopexy as determined by the investigator.

Rhegmatogenous retinal detachment or macular hole	
Discontinue study treatment and withdraw the patient from the study if rhegmatogenous retinal detachment or Stage 3 or 4 macular hole is observed.

Central serous retinopathy	
Interrupt study treatment if serous retinopathy is present in the study eye. Study treatment may be resumed upon resolution.

Table 1 Dose-Interruption, Treatment-Discontinuation, and Study-Withdrawal Criteria (cont.)

Event	Dose-Interruption, Treatment-Discontinuation, Study-Withdrawal Criteria
Active infection	
Interrupt study treatment if any of the following are present: infectious conjunctivitis, infectious keratitis, infectious scleritis, or endophthalmitis in either eye; or if the patient is currently receiving systemic treatment for an active infection.
 
Patients with endophthalmitis in the study eye will discontinue the study treatment and be withdrawn from the study.

Cataract surgery in study eye	
Interrupt study treatment after cataract surgery in study eye. Study treatment may be resumed no earlier than 30 days after an uncomplicated cataract surgery and no evidence of post-operational inflammation. For cataract surgery with complications, study treatment may be permitted as determined by the Sponsor and investigator.

Oral corticosteroids (prednisone > 10 mg/day or equivalent)	
Interrupt study treatment. Study treatment may be resumed when oral corticosteroids dosing is prednisone ≤ 10 mg/day or equivalent.

IV corticosteroids	
Interrupt study treatment. Study treatment may be resumed when the patient has finished IV corticosteroid course and oral corticosteroid dosing is prednisone ≤ 10 mg/day or equivalent.

BCVA = best corrected visual acuity; IOP = intraocular pressure; IV = intravenous; VA = visual acuity.

5.2 SAFETY PARAMETERS AND DEFINITIONS

Safety assessments will consist of monitoring and recording adverse events, including serious adverse events and adverse events of special interest, *performing protocol-specified safety laboratory assessments*, and other protocol-specified tests that are deemed critical to the safety evaluation of the study.

Certain types of events require immediate reporting to the Sponsor, as outlined in Section 5.4.

5.2.1 Adverse Events

According to the ICH guideline for GCP, an adverse event is any untoward medical occurrence in a clinical, investigational, patient-administered pharmaceutical product, regardless of causal attribution. An adverse event can therefore be any of the following:

- Any unfavorable and unintended sign (including an abnormal laboratory finding), symptom, or disease temporally associated with the use of a medicinal product, whether or not considered related to the medicinal product

- Any new disease or exacerbation of an existing disease (a worsening in the character, frequency, or severity of a known condition), except as described in Section [5.3.5.9](#)
- Recurrence of an intermittent medical condition (e.g., headache) not present at baseline
- Any deterioration in a laboratory value or other clinical test (e.g., electrocardiogram, X-ray) that is associated with symptoms or leads to a change in study treatment or concomitant treatment or discontinuation from study drug
- Adverse events that are related to a protocol-mandated intervention, including those that occur prior to study drug administration (e.g., screening invasive procedures, such as biopsies)

5.2.2 Serious Adverse Events (Immediately Reportable to the Sponsor)

A serious adverse event is any adverse event that meets any of the following criteria:

- Is fatal (i.e., the adverse event actually causes or leads to death)
- Is life threatening (i.e., the adverse event, in the view of the investigator, places the patient at immediate risk of death)
 - This does not include any adverse event that had it occurred in a more severe form or was allowed to continue might have caused death.
- Requires or prolongs inpatient hospitalization (see Section [5.3.5.10](#))
- Results in persistent or significant disability/incapacity (i.e., the adverse event results in substantial disruption of the patient's ability to conduct normal life functions)
- Is a congenital anomaly/birth defect in a neonate/infant born to a mother exposed to study drug
- Is a significant medical event in the investigator's judgment (e.g., may jeopardize the patient or may require medical/surgical intervention to prevent one of the outcomes listed above)

The terms “severe” and “serious” are not synonymous. Severity refers to the intensity of an adverse event (e.g., rated as mild, moderate, or severe; see Section [5.3.3](#)); the event itself may be of relatively minor medical significance (such as severe headache without any further findings).

Severity and seriousness need to be independently assessed for each adverse event recorded on the eCRF.

Serious adverse events are required to be reported by the investigator to the Sponsor immediately (i.e., no more than 24 hours after learning of the event; see Section [5.4.2](#) for reporting instructions).

5.2.3 Adverse Events of Special Interest (Immediately Reportable to the Sponsor)

Adverse events of special interest are required to be reported by the investigator to the Sponsor immediately (i.e., no more than 24 hours after learning of the event; see Section 5.4.2 for reporting instructions). Adverse events of special interest for this study include the following:

- Cases of potential drug-induced liver injury that include an elevated ALT or AST in combination with either an elevated bilirubin or clinical jaundice, as defined by Hy's law (see Section 5.3.5.6)
- Suspected transmission of an infectious agent by the study drug, as defined below
Any organism, virus, or infectious particle (e.g., prion protein transmitting transmissible spongiform encephalopathy), pathogenic or non-pathogenic, is considered an infectious agent. A transmission of an infectious agent may be suspected from clinical symptoms or laboratory findings that indicate an infection in a patient exposed to a medicinal product. This term applies only when a contamination of the study drug is suspected.
- Adverse events resulting from medication error
Examples of medication errors include, but are not limited to, overdose, incorrect dose, incorrect route, incorrect drug, incorrect administration, or incorrect kit.
If the medication error did result in an adverse event, the primary event term should reflect the adverse event that occurred as a result of the medication error and identify it in "other suspected causes of serious adverse event/adverse event" data field as a medication error.
- Sight-threatening adverse events: An adverse event is considered to be *serious and* sight threatening and should be reported expeditiously if it meets one or more of the following criteria:
 - It causes a decrease of ≥ 30 letters in VA score (compared with the last assessment of VA prior to the most recent assessment) lasting more than 1 hour.
 - It requires surgical intervention (i.e., conventional surgery, vitreous tap, or biopsy with *intravitreal* injection of anti-infective agents, or laser or retinal cryopexy with gas) to prevent permanent loss of sight.
 - It is associated with severe intraocular inflammation (i.e., endophthalmitis, 4+ anterior chamber cell/flare or 4+ vitritis; see Section 5.3.5 and Appendix 3 for intraocular inflammation grading scales).
 - In the opinion of the investigator, it may require medical intervention to prevent permanent loss of sight.

All above listed sight-threatening adverse events should be reported as serious events, listing the underlying cause (if known) of the event as the primary event term.

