4.6.2 Study Treatment Discontinuation

Patients must permanently discontinue study treatment if they experience any of the following:

- *Any medical condition that the investigator or Sponsor determines may jeopardize the patient's safety if he or she continues to receive study treatment*
- Pregnancy

The investigator has the right to discontinue a patient for reasons of non-compliance (e.g., missed doses and/or visits) or if the investigator or Sponsor determines it is in the best interest of the patient. The primary reason for the treatment discontinuation should be recorded on the appropriate eCRF.

Patients who must discontinue treatment will not be replaced or allowed to restart the study treatment. Any patient discontinued from study treatment will also be discontinued from the study and will not be allowed to re-enter the study; the patient will be encouraged to undergo a study early termination visit.

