5.3.5.9 Worsening of Geographic Atrophy *in Study Eye*

Medical occurrences or symptoms of deterioration that are anticipated as part of the normal progression of GA of the study eye should be recorded as an adverse event only if judged by the investigator to have unexpectedly worsened in severity or frequency or changed in nature at any time during the study. When recording an unanticipated worsening of GA in the study eye on the Adverse Event eCRF, it is important to convey the concept that the condition has changed by including applicable descriptors (e.g., “accelerated Geographic Atrophy”).

Events that are clearly consistent with the expected pattern of progression of the underlying disease *in the study eye* should not be recorded as adverse events. The expedited reporting requirements for sight-threatening events (listed in the Section 5.2.3) *still* apply to these unexpected changes in the study eye GA.

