Appendix 2 Study Flowchart: **Unscheduled Safety Assessment Visit**

Assessments ^a
Vital signs (blood pressure, respiration rate, pulse, and temperature)
Best corrected visual acuity (4-m starting distance) ^b
Slit-lamp examination
Dilated binocular indirect high-magnification ophthalmoscopy
IOP ^c
Adverse events ^d
Concurrent ocular procedures
Concomitant medications

IOP = intraocular pressure.

^a If determined to be necessary by the investigator, perform the listed assessments. All ocular assessments should be performed on both eyes.

^b Perform finger-counting test followed by hand-motion and light-perception tests when necessary.

^c The method used for the IOP measurement for a patient must remain consistent throughout the study.

^d Adverse event causality to be evaluated by the qualified ophthalmologist.

Appendix 3

Grading Scale for Assessment of Anterior Chamber Flare or Cells and Vitreous Cells

Table 1 Grading Scale for Anterior Chamber Flare or Cells

Grade	Description
Flare	
0	No protein is visible in the anterior chamber when viewed by an experienced observer using slit lamp biomicroscopy; a small, bright, focal slit beam of white light; and high magnification.
Trace	Trace amount of protein is detectable in the anterior chamber. This protein is visible only with careful scrutiny by an experienced observer using slit lamp biomicroscopy; a small, bright, focal slit beam of white light; and high magnification.
1+	Slight amount of protein is detectable in the anterior chamber. The presence of protein in the anterior chamber is immediately apparent to an experienced observer using slit lamp biomicroscopy and high magnification, but such protein is detected only with careful observation with the naked eye and a small, bright, focal slit-beam of white light.
2 to 3+	Moderate amount of protein is detectable in the anterior chamber. These grades are similar to 1+, but the opacity would be readily visible to the naked eye of an observer using any source of a focused beam of white light. This is a continuum of moderate opacification, with 2+ being less apparent than 3+.

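### The 30-letter criterion in 5.2.3 resets at every VA check, so a stepwise loss across undosed checks may never meet it

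*Combined protocol and SAP*

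**What the plan says.** Section 5.2.3 lists four ways in which an adverse event becomes sight-threatening, and so reportable as serious within 24 hours. The first is a loss of at least 30 letters, "compared with the last assessment of VA prior to the most recent assessment) lasting more than 1 hour". The others are surgical intervention to save sight, severe intraocular inflammation, and an investigator judgment: "In the opinion of the investigator, it may require medical intervention to prevent permanent loss of sight".

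Table 1 in 5.1.2 also uses 30 letters, to interrupt dosing. It applies to a treatment-related decrease in study-eye BCVA, "compared with the last assessment of BCVA prior to the most recent treatment".

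VA can be checked without a dose in two ways:

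- **Interrupted dosing.** Once a Table 1 criterion is met, "treatment will be interrupted (or discontinued, if applicable) and will not be resumed earlier than the next scheduled study visit". The criteria include inflammation of 1+ or more, vitreous hemorrhage and IOP of 30 mmHg or more. Appendix 1 schedules BCVA at every treatment visit. Withdrawal is considered only after more than three consecutive missed doses within 6 months.
- **Unscheduled safety visits.** Appendix 2 lists BCVA among the assessments, with the note "If determined to be necessary by the investigator, perform the listed assessments".

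Two general rules can also bring a case to the Sponsor. Section 5.2.2 includes events the investigator finds medically significant and any event that "Results in persistent or significant disability/incapacity". Section 5.3.5.3 requires a persistent event that becomes serious to be reported within 24 hours.

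**The concern.** The letter criterion is the only one of the 5.2.3 criteria that rests on a measured VA value. Its reference is whatever VA was recorded last, so each extra check resets it. Patients with an ocular complication are the likely ones to have extra checks, because their dosing is interrupted or they are called back. Closer monitoring can then divide a large loss into steps that are each below 30 letters.

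Meeting Table 1 does not close the gap. Table 1 governs dosing, covers only the study eye and treatment-related loss, and does not itself start 24-hour reporting. At stake is the timeliness of serious-event reporting for a vision loss that the protocol's own threshold marks as severe. No estimate or test is at stake.

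**Working it through.** The plan gives no figure to reproduce on this point. The check applies both reference rules to the Appendix 1 visit grid and to illustrative letter scores, which are assumptions.

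**Inputs.** Threshold 30 letters (5.2.3 and Table 1). BCVA at every treatment visit: Weeks 4 to 96 every 4 weeks, 24 visits after Day 1; Weeks 6 to 96 every 6 weeks, 16 visits (Appendix 1). Up to 1800 patients (3.1.2).

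**1. Where the references differ.** At each check, compare the previous VA assessment with the last VA before the most recent dose.

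| Situation | Q4W | Q6W |
|---|---|---|
| All doses given, no extra check | 0 of 24 | 0 of 16 |
| One unscheduled VA check | 1 of 25 | 1 of 17 |
| Three consecutive doses missed, visits attended | 3 of 24 | 3 of 16 |

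**2. Example.** VA is 70 at a dosed visit, then 50 and 30 at two undosed checks.

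- Against the previous check: 70 − 50 = 20 and 50 − 30 = 20. Neither reaches 30.
- Against the pre-dose value: 70 − 30 = 40. This exceeds 30.

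**3. Largest loss that can escape the letter criterion.** Each step can be at most 29 letters, so with n checks after the dose the bound is 29n: 29 for one check, 58 for two, 87 for three.

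**4. Illustration of a divided loss.** Suppose a total loss L falls at random across k checks after one dose, with letters treated as continuous. The chance that no step reaches 30 is the sum over j of (−1)^j C(k,j) max(0, 1 − 30j/L)^(k−1).

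- k = 2, which reduces to (60 − L)/L for L from 30 to 60: L = 35 gives 25/35 = 71%; L = 40 gives 20/40 = 50%; L = 50 gives 10/50 = 20%; L = 60 gives 0.
- k = 3, which reduces to 1 − 3(1 − 30/L)² for the same range: L = 35 gives 94%; L = 40 gives 81%; L = 50 gives 52%; L = 60 gives 25%.
- k = 1: a loss of 30 letters or more is never missed.

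These values show how the rule behaves. Nothing in the documents supports the random split, so they are not risk estimates.

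**5. Why the current reference must stay.** Take 40 at a dosed visit, 70 at an undosed check, then 35. The drop from the previous check is 70 − 35 = 35, but from the pre-dose value only 40 − 35 = 5. Replacing one reference with the other would lose this case.

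**6. False flags from adding the second reference.** In a stable eye with independent normal test error, a difference of two tests has standard deviation SD × √2. The chance of a spurious drop of 30 or more is P(Z ≥ 30/(SD√2)). With an assumed SD of 5 this is P(Z ≥ 4.24) = 1.1 × 10⁻⁵; with SD 3 it is 7.7 × 10⁻¹³. One to five added comparisons in each of 1800 patients make 1,800 to 9,000 comparisons, so at SD 5 the expected total is 0.02 to 0.10.

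**The case against.** The case for leaving the text alone has four parts.

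- **The regular schedule is unaffected.** This stands. The gap needs an extra check, a cumulative loss of at least 30 letters, and every step below 30.
- **Other criteria apply.** Investigator opinion is a low bar, a medically significant event is serious under 5.2.2, and 5.3.5.3 covers a known complication that worsens. This largely stands. All three need a judgment, however, and none is tied to a measured VA threshold.
- **The two rules have different purposes.** Table 1 is about dosing; 5.2.3 covers any adverse event in either eye, and its one-hour condition suggests acute loss. A different reference is therefore not an error in itself. That is fair, but the documents give no reason for a reference that weakens as checks become more frequent.
- **The Sponsor gets a record anyway.** If the loss is judged treatment-related, Table 1 interrupts dosing and the reason goes on an eCRF. That record is not necessarily made within 24 hours.

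A reader might go further and infer that the VA safety summaries hide severe loss in withdrawn patients, since "Any patient discontinued from study treatment will also be discontinued from the study and will not be allowed to re-enter the study". The documents do not support that. Section 6.3 places the VA summary in the population with at least one dose. Withdrawn patients are asked back for an early termination visit that includes BCVA (4.6, Appendix 1), and the adverse event results still count their events. A letter-loss proportion would also mix in ordinary decline from geographic atrophy. That no such proportion is stated is a matter of detail, and the Data Analysis Plan cited in 6.4 is not available to check.

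**Conclusion.** The gap is real but narrow. When VA is checked without a dose, a stepwise loss of 30 or more letters since the last pre-dose value can fail the 5.2.3 letter criterion at every check. Expedited serious reporting then depends on judgment-based criteria, which will catch many such cases but not necessarily all.

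The number of patients affected cannot be derived from the documents. It is probably small, because several conditions must coincide. A reader might take the percentages in the working as the share of severe losses that would go unreported. They are not: they assume a random split, condition on two or three checks after one dose, and ignore every other reporting route.

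The planned analyses are not put in doubt. The case for a change is that a measured safety threshold should not become harder to meet as monitoring becomes closer, and that correcting it is cheap.

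**What to change.** In 5.2.3, count a decrease of at least 30 letters compared with either the previous VA assessment or the last VA assessment before the most recent study treatment. Keep the one-hour condition and the other three criteria. The added reference is a date, so it also works for the fellow eye, where Appendix 1 has ocular assessments done in both eyes unless noted otherwise.

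The cost is one phrase and a few more expedited reports, with no new visits. Test noise should add almost none of those reports (step 6 of the working).

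The change does not reach slow loss across successive dosed visits, where the pre-treatment reference also moves. Part of that loss is covered by 5.3.5.9, which keeps out of adverse event recording "Events that are clearly consistent with the expected pattern of progression of the underlying disease" in the study eye.

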5.3 METHODS AND TIMING FOR CAPTURING AND ASSESSING SAFETY PARAMETERS

The investigator is responsible for ensuring that all adverse events (see Section 5.2.1 for definition) are recorded on the Adverse Event eCRF and reported to the Sponsor in accordance with instructions provided in this section and in Sections 5.4–5.6.

For each adverse event recorded on the Adverse Event eCRF, the investigator will make an assessment of seriousness (see Section 5.2.2 for seriousness criteria), severity (see Section 5.3.3), and causality (see Section 5.3.4).

5.3.1 Adverse Event Reporting Period

Investigators will seek information on adverse events at each patient contact. All adverse events, whether reported by the patient or noted by study personnel, will be recorded in the patient’s medical record and on the Adverse Event eCRF.

After completion of the Week 96 visit of the parent study and informed consent for the extension study has been obtained, any adverse events that are ongoing or started after the Week 96 visit of the parent study should be reported on the extension study Adverse Event eCRF.

All adverse events will be reported until *at least 30 days after the last dose of study drug or the last study visit, whichever is later*. After this period, the investigator should report any serious adverse events that are believed to be related to prior study drug treatment (see Section 5.6).

